
Section 13.6.3 Secondary Endpoints p. 118-120 (Continued)
	
seizure-free days, number of seizures by subtype, number of infantile/epileptic spasms, use of rescue medication, number of episodes of status epilepticus, Vineland-II, Wechsler scales, CBCL, ABCL, SCQ, QOLCE, QOLIE-31-P, SGIC/CGIC and PGIC scores, the data will be summarized at baseline and over the treatment period, and at each time point (or 28-day period, as appropriate) during the maintenance period. Changes from baseline to the average over the treatment period (or at end of study) will be analyzed using ANCOVA, as with the primary endpoint (or appropriate non-parametric methods if data are found to be not normally distributed). SGIC-SD/CGIC-SD assessments recorded at the end of treatment will be analyzed with ordinal logistic regression using the proportional odds model. Changes from baseline for IGF-1 levels will be summarized by treatment group and plotted against the Tanner Stages, weight, and height. Tanner Stages will be evaluated and summarized descriptively at each time point in terms of frequency
	
Cochran–Mantel–Haenszel test stratified by age group. In addition, the difference in proportions and the odds ratio, together with 95% CIs, comparing the treatment groups will be presented.
 
For changes in composite focal seizure score, number of seizure-free days, use of rescue medication, number of episodes of status epilepticus (only if there is a sufficient number of patients with data), Vineland-II, Wechsler scales, CBCL, ABCL, SCQ, QOLCE and QOLIE-31-P scores, the data will be summarized at baseline and over the treatment period, and at each time point (or 28 day period, as appropriate) during the maintenance period. Changes from baseline to the average over the treatment period (or at end of study) will be analyzed using ANCOVA (or appropriate non-parametric methods if data are found to be not normally distributed). The models will include baseline and age group as covariates and treatment group as fixed factor. The treatment difference, together with the 95% confidence intervals (CIs) will be presented. The percentage change in total seizures, the number
	
See Section 2.3

Revised Protocol Section Number, Heading and Page Number	Original Wording from Clinical Protocol Version 2 Date 21 OCT 2015 (Deleted wording is struck through and in bold)	Revised Wording from Clinical Protocol Amendment 2 (Clinical Protocol V3 25Aug16) (Revised wording is underscored and in bold)	Rationale for the amendment

Section 13.6.3 Secondary Endpoints p. 118-120 (Continued)
	
and proportions. Number (%) of patients with changes in Tanner Stages will be summarized by treatment group.
 
The primary efficacy analysis uses the ITT analysis set over the evaluable period. ANCOVA analysis, using the LOCF approach, will be used to handle missing values.
 
In order to explore the robustness of the primary analysis, further sensitivity analysis (in addition to that already detailed in Section 13.6.2.1) may be specified in the SAP.
 
Similar approaches, using the LOCF, will be applied if the data are analyzed using non-parametric methods.
	
of seizures (average per 28 days) by subtype and the number of ‘other’ seizures (average per 28 days) will be analyzed using a Wilcoxon rank-sum test as per the primary endpoint.
 
SGIC-SD/CGIC-SD, SGIC/CGIC and PGIC assessments recorded at the end of treatment will be analyzed with ordinal logistic regression using the proportional odds model.
 
Changes from baseline for IGF-1 levels will be summarized by treatment group and plotted against the Tanner Stages, weight, and height.
 
Tanner Stages will be evaluated and summarized descriptively at each time point in terms of frequency and proportions. Number (%) of patients with changes in Tanner Stages will be summarized by treatment group.
 
In order to explore the robustness of the primary analysis, further sensitivity analysis (in addition to that already detailed in Section 13.6.2.1) may be specified in the SAP.
	
See Section 2.3

Revised Protocol Section Number, Heading and Page Number	Original Wording from Clinical Protocol Version 2 Date 21 OCT 2015 (Deleted wording is struck through and in bold)	Revised Wording from Clinical Protocol Amendment 2 (Clinical Protocol V3 25Aug16) (Revised wording is underscored and in bold)	Rationale for the amendment
Section 13.6.4 Pharmacokinetics p. 120	Plasma concentrations for CBD, THC and their major metabolites, following single and multiple doses of GWP42003-P will be summarized by treatment group. Estimates of PK parameters will also be summarized using the appropriate statistics.	Plasma concentrations for CBD and its major metabolites, following single and multiple doses of GWP42003-P will be summarized by treatment group. Estimates of PK parameters will also be summarized using the appropriate statistics.	See Section 2.4
Appendix 1 Schedules of Assessments	< Changes to the table of Schedules of Assessments (Blinded Phase and OLE) are shown in Appendix 1 > (...) *Telephone safety calls will be completed every two days during titration, one week after the end of titration and, for patients not entering the OLE, weekly from Visit 10 to Visit 12.	< Changes to the table of Schedules of Assessments (Blinded Phase and OLE) are shown in Appendix 1 > (...) *Telephone safety calls will be completed every two days during titration, one week after the end of titration and, for patients not entering the OLE, weekly from Visit 10 to Visit 12. If the call falls on a weekend, it is permitted to schedule the call for the Friday before or Monday after the weekend instead. ∞ In countries where controlled drugs can only be	See Section 2.1 , Section 2.2 , Section 2.8 , See Section 2.10

Revised Protocol Section Number, Heading and Page Number	Original Wording from Clinical Protocol Version 2 Date 21 OCT 2015 (Deleted wording is struck through and in bold)	Revised Wording from Clinical Protocol Amendment 2 (Clinical Protocol V3 25Aug16) (Revised wording is underscored and in bold)	Rationale for the amendment
Appendix 1 Schedules of Assessments (Continued)		
dispensed for a maximum of 28 days, there will not be a +3 day visit window, only a -3 day visit window.
 
*Only for patients weighing > 20 kg
	

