APPENDIX 1 AMENDED FIGURES AND TABLES

Amended Figure from Clinical Protocol V4 05Dec16

(Deleted wording is struck through and in bold; amended wording is underlined and in bold)

Table 8.1.2-2

Table 8.1.2-2 Blinded Transition						
	Patients randomised to 25 mg/kg/day group		Patients randomised to 50 mg/kg/day group		Patients randomised to placebo group	
Day Blinded Transition/OLE	Blinded	Open label	Blinded	Open label	Placebo	Open label
1	25	0	50	0	0	0
2	22.5	0	45	0	0	0
3	20	5	40	5	0	5
4	17.5	5	35	5	0	5
5	15	10	30	10	0	10
6	12.5	10	25	10	0	10
7	10	15	20	15	0	15
8	7.5	15	15	15	0	15
9	5	20	10	20	0	20
10	2.5	20	5	20	0	20
11	0	25	0	25	0	25
12	0	25	0	25	0	25
13	0	25	0	25	0	25
14	0	25	0	25	0	25

Table 8.1.2 – 3 OLE Titration Schedule

OLE Day	Blinded Dose (mg/kg/day)
15 (Visit B2)	26.25
16	27.5
17	30
18	30
19	32.5
20	32.5
21	35
22	35
23	37.5
24	37.5
25	40
26	40
27	42.5
28	42.5
29	45
30	45
31	47.5
32	47.5
33	50
34	50
35	50
36 (Visit B3)	50

Study Title: A double-blind, randomized, placebo-controlled study to investigate the efficacy and safety of cannabidiol (GWP42003-P, CBD) as add-on therapy in patients with tuberous sclerosis complex who experience inadequately-controlled seizures

Study Code: GWEP1521

EudraCT Number: 2015-002154-12

CLINICAL PROTOCOL AMENDMENT NUMBER: 2

**to be incorporated into the Protocol, creating
CLINICAL PROTOCOL V3 25Aug16**

**GW Research Ltd
[name]
United Kingdom**

Tel: PPD
Fax: PPD

Confidentiality Statement

This document contains confidential information of GW Research Ltd (GW) that must not be disclosed to anyone other than the recipient study staff and members of the institutional review board or independent ethics committee. This information cannot be used for any purpose other than the evaluation or conduct of the clinical investigation without the prior written consent of GW.

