Section 5.3.4 Investigational Medicinal Product Accountability p. 56	(...) IMP will be dispensed at Visits 3, 4, 5, 7 and 9 during the blinded phase and Visits B1, B2, B3 and B4 and every three months thereafter during the OLE. Patients will be asked to return all IMP (used and unused) to each subsequent visit.	(...) IMP will be dispensed at Visits 3, 4, 5, 6 , 7, 9 and 10 (patients not entering the OLE) during the blinded phase and Visits B1, B2, B3, B4, B5, B6, B7, B8 and B9. In countries where controlled drugs can only be dispensed for a maximum of 28 days, arrangements must be made with patients (or their caregivers) to come in every 4 weeks to be dispensed further GWP42003-P and return of used/unused GWP42003-P. All patients will be asked to return all IMP (used and unused) to each subsequent visit.	See Section 2.10 See Section 2.8
Section 5.3.5 Post-trial Provision p. 56	Following completion of the blinded phase patients will be invited to continue to receive GWP42003-P in an open label extension study. The open label extension will continue until market authorization is granted for GWP42003-P in TSC.		See Section 2.1
Section 6.1	(...)	(...)	

Revised Protocol Section Number, Heading and Page Number	Original Wording from Clinical Protocol Version 2 Date 21 OCT 2015 (Deleted wording is struck through and in bold)	Revised Wording from Clinical Protocol Amendment 2 (Clinical Protocol V3 25Aug16) (Revised wording is underscored and in bold)	Rationale for the amendment
Inclusion Criteria p. 58	6.1.4 Well-documented history of epilepsy, with compatible electroencephalogram (EEG) and clinical history.	6.1.4 Well-documented clinical history of epilepsy.	See Section 2.10
Section 6.2.7 p.59	Patient is taking felbamate, and they have been taking it for less than one year prior to screening.	Patient has been taking felbamate for less than one year prior to screening.	See Section 2.7
Section 6.2.11 p.59	Active suicidal plan/intent in the past six months, or a history of suicide attempt in the last two years, or more than one lifetime suicide attempt.	Any history of suicidal behavior or any suicidal ideation of type 4 or 5 on the C-SSRS in the last month or at screening.	See Section 2.10
Section 6.2.12 p. 59	C-SSRS grade 4 or 5 at screening.		See Section 2.10

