Revised Protocol Section Number, Heading and Page Number	Original Wording from Clinical Protocol Version 2 Date 21 OCT 2015 (Deleted wording is struck through and in bold)	Revised Wording from Clinical Protocol Amendment 2 (Clinical Protocol V3 25Aug16) (Revised wording is underscored and in bold)	Rationale for the amendment
Section 9.1.1.4 Visit 4 (Day 15) p. 69	(...) The PGIC and SGIC/CGIC will also be performed. Suicidality will be assessed using the C-SSRS/ Children’s C-SSRS (Since Last Visit) or, in patients with profound cognitive impairment, by interview and clinical judgment. (...) Following Visit 4, during titration, safety telephone calls must be made every two days.	(...) Suicidality will be assessed using the C-SSRS/ Children’s C-SSRS (Since Last Visit) or, in patients with profound cognitive impairment, by interview and clinical judgment. (...) Following Visit 4, during titration, safety telephone calls must be made every two days. If the call falls on a weekend, it is permitted to schedule the call for the Friday before or Monday after the weekend instead.	See Section 2.2 See Section 2.10
Section 9.1.1.5 Visit 5 (Day 29) p.70	The following observations will be made at Visit 5: concomitant medications, (including AEDs), physical examination (including height and body weight), ECG, vital signs, epilepsy-related hospitalizations and AEs. Clinical laboratory samples (blood and urine [where possible]), will be taken for hematology, biochemistry and urinalysis.	The following observations will be made at Visit 5: concomitant medications, (including AEDs), physical examination (including height and body weight), ECG, vital signs, postural BP , epilepsy-related hospitalizations and AEs. Clinical laboratory samples (blood and urine [where possible]), including a pregnancy test if appropriate (using both a serum sample and a urine dipstick) , will be taken for hematology, biochemistry and	See Section 2.10 See Section 2.9

Revised Protocol Section Number, Heading and Page Number	Original Wording from Clinical Protocol Version 2 Date 21 OCT 2015 (Deleted wording is struck through and in bold)	Revised Wording from Clinical Protocol Amendment 2 (Clinical Protocol V3 25Aug16) (Revised wording is underscored and in bold)	Rationale for the amendment

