Section 9.1.1.9 Visit 9 (Day 85) p. 72	
(...) Clinical laboratory samples (blood and urine [where possible]), will be taken for hematology, biochemistry and urinalysis.
 
(...) The PGIC and SGIC/CGIC will also be performed. Suicidality will be assessed using the C-SSRS/ Children’s C-SSRS (Since Last Visit) or, in patients with profound cognitive impairment, by interview and clinical judgment.
	
(...) Clinical laboratory samples (blood and urine [where possible]), including a pregnancy test if appropriate (using both a serum sample and a urine dipstick), will be taken for hematology, biochemistry and urinalysis.
 
(...) Suicidality will be assessed using the C-SSRS/ Children’s C-SSRS (Since Last Visit) or, in patients with profound cognitive impairment, by interview and clinical judgment.
	
See Section 2.9
 
See Section 2.2

Revised Protocol Section Number, Heading and Page Number	Original Wording from Clinical Protocol Version 2 Date 21 OCT 2015 (Deleted wording is struck through and in bold)	Revised Wording from Clinical Protocol Amendment 2 (Clinical Protocol V3 25Aug16) (Revised wording is underscored and in bold)	Rationale for the amendment
Section 9.1.1.10 Visit 10 (Day 113, End of Treatment/Withdrawal Visit) p. 72-73	(...) 
A visit window of ± 3 days from the scheduled visit date is permitted, but it is preferred that the visit is performed on the scheduled visit day where possible.
 (...) 
(...) Clinical laboratory samples (blood and urine [where possible]) will be taken for hematology, biochemistry, urinalysis, a urine THC screen, determination of serum IGF 1 levels (for patients less than 18 years of age) and a pregnancy test (using a serum sample, if appropriate), to be performed by the central laboratory.
	(...) 
A visit window of ± 3 days from the scheduled visit date is permitted, but it is preferred that the visit is performed on the scheduled visit day where possible. In countries where controlled drugs can only be dispensed for a maximum of 28 days, there will not be a +3 day visit window, only a -3 day visit window.
 (...) 
Clinical laboratory samples (blood and urine [where possible]) will be taken for hematology, biochemistry, urinalysis, determination of serum IGF 1 levels (for patients less than 18 years of age) and a pregnancy test (using a serum sample, if appropriate), to be performed by the central laboratory.
	See Section 2.10 See Section 2.8

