
Section 9.1.2.1 Visit B1 (Day 1) p. 75-76
	
(...) Day 1 is regarded as the first day of IMP dosing. The following data collected at the ‘End of Treatment’ visit of the blinded phase will also be considered as Visit B1 data: vital signs, physical examination (including height and body weight), details of menstruation (for females), Tanner Staging (patients aged 10–17 [inclusive]), ECG, clinical laboratory samples (including THC screen), serum IGF-1 levels (patients less than 18 years of age) and pregnancy test (if appropriate), IVRS and paper diary information from the blinded phase (including information regarding seizures, AEs, usage of rescue medication, concomitant AEDs, IMP dosing), epilepsy-related hospitalizations, concomitant medications and/or changes to medication, suicidality, QOLCE/QOLIE-31-P, PGIC, SGIC/CGIC, SGIC-SD/CGIC-SD, Wechsler Tests, CBCL/ABCL, SCQ and the Vineland-II. A pregnancy test (if appropriate) must be conducted. (...) In addition, patients/caregivers will be instructed to complete a weekly seizure reporting diary until the ‘End of Treatment’/withdrawal visit using the IVRS.
	
(...) Day 1 is regarded as the first day of IMP dosing. The following data collected at the ‘End of Treatment’ visit of the blinded phase will also be considered as Visit B1 data: vital signs, physical examination (including height and body weight), details of menstruation (for females), Tanner Staging (patients aged 10–17 [inclusive]), ECG, clinical laboratory samples, serum IGF-1 levels (patients less than 18 years of age) and pregnancy test (if appropriate), IVRS and patient diary information from the blinded phase (including information regarding seizures, AEs, usage of rescue medication, concomitant AEDs, IMP dosing), epilepsy-related hospitalizations, concomitant medications and/or changes to medication, suicidality, QOLCE/QOLIE-31-P, PGIC, SGIC/CGIC, SGIC-SD/CGIC-SD, Wechsler Tests, CBCL/ABCL, SCQ and the Vineland-II. (...) In addition, patients/caregivers will be instructed to complete a weekly seizure reporting diary until the Follow-up visit using the IVRS.
	
See Section 2.8
 
See Section 2.10

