Section 9.1.1.3 Visit 3 (Day 1, Randomization) p. 63–64 (continued)	
examination (including height and body weight), ECG, vital signs, epilepsy-related hospitalizations and AEs.
 
Clinical laboratory samples (blood and urine [where possible]) will be taken for hematology, biochemistry and urinalysis.
 
(...) The PGIC, SGIC/CGIC and Vineland-II will also be performed.
	
examination (including height and body weight), details of menstruation (for females), Tanner Staging (for patients aged 10–17 years [inclusive], or earlier if clinically indicated by onset of menarche or other signs of precocious puberty), ECG, vital signs, postural blood pressure, epilepsy-related hospitalizations, AEs and paper diary review. The ECG will be repeated four hours after the first dose of IMP. The investigator will verify that the ESC has confirmed the diagnosis of TSC.
 
Clinical laboratory samples (blood and urine [where possible]) will be taken for hematology, biochemistry, urinalysis, a urine THC screen, determination of serum IGF-1 levels (for patients less than 18 years of age) and a pregnancy test if appropriate (using both a serum sample and a urine dipstick).
 
(...) PK samples (patients >20 kg in weight only) will be taken following randomization and at two hours and
	

Revised Protocol Section Number, Heading and Page Number	Original Wording from Clinical Protocol Version 1, Date 16 Jun 15 (Deleted wording is struck through and in bold)	Revised Wording from Clinical Protocol Amendment 1 (Clinical Protocol Version 2, Date 21 Oct 15) (Revised wording is underscored and in bold)	Rationale for the amendment

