Section 9.1.1.3 Visit 3 (Day 1, Randomization) p. 63–64 (continued)	(...) The investigator must assess adherence to the titration regimen by reviewing the patient's diary and IVRS data and record the patient's attendance at the visit. All IMP (used and unused) will be collected and a check of the returned IMP against usage should be made. Patients will then receive a new treatment pack of the IMP.	QOLCE/QOLIE-31-P, Wechsler Tests, CBCL/ABCL, SCQ and the Vineland-II. (...) Patients/caregivers will be asked to write a brief description of their/the patient's overall condition and assess the average duration of seizure subtypes as a memory aid for the SGIC/CGIC and SGIC-SD/CGIC-SD; these will be referred to at relevant, subsequent visits or withdrawal. IMP will be dispensed for the following two weeks and patients or their caregivers will be provided with individual dosing schedules as described in Section 8.1. Each patient will then receive a titration regimen. The first dose of IMP will be administered in clinic. Patients or their caregivers will be instructed on how to record the diary information, including both the paper and IVRS diaries. Provided that the risk/benefit outcome is favorable in the investigator's opinion, a blood sample will be collected prior to administration of IMP to determine	

Revised Protocol Section Number, Heading and Page Number	Original Wording from Clinical Protocol Version 1, Date 16 Jun 15 (Deleted wording is struck through and in bold)	Revised Wording from Clinical Protocol Amendment 1 (Clinical Protocol Version 2, Date 21 Oct 15) (Revised wording is underscored and in bold)	Rationale for the amendment
	
(...)
 
(...)
	
plasma concentrations of concomitant AEDs. (...) A further call must be completed one week after the end of titration. (...)
	

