Section 9.1.1.10 Visit 10 (Day 113, End of Treatment/ Withdrawal Visit) p. 67–69 (continued)	(...) (...) All IMP (used and unused) will be collected and a check of the returned IMP against usage should be made. The patient diaries will be collected.	SGIC-SD/CGIC-SD, Wechsler Tests, CBCL/ABCL, SCQ and the Vineland-II. (...) The investigator must assess adherence to the dosing regimen by reviewing the patient’s diary and IVRS data, record the patient’s attendance at the visit and confirm the outcome of the visit. All IMP (used and unused) will be collected and a check of the returned IMP against usage should be made. (...) For patients who withdraw early, the IVRS will be contacted to confirm withdrawal from the study. Patients who withdraw should have their dose of IMP tapered gradually (10% each day) over a period of 10 days, beginning at the time the decision is made to discontinue. In some cases, tapering the dose of IMP may be inadvisable (e.g., continued dosing is not possible due to an AE). The decision on whether or not to taper IMP will be	

Revised Protocol Section Number, Heading and Page Number	Original Wording from Clinical Protocol Version 1, Date 16 Jun 15 (Deleted wording is struck through and in bold)	Revised Wording from Clinical Protocol Amendment 1 (Clinical Protocol Version 2, Date 21 Oct 15) (Revised wording is underscored and in bold)	Rationale for the amendment
Section 9.1.1.10 Visit 10 (Day 113, End of Treatment/ Withdrawal Visit) p. 67–69 (continued)		
left to the investigator’s clinical judgment. If tapering is undertaken, a 10-day supply of IMP (if required) and instructions for tapering the dose will be provided. Patients should continue to complete the IVRS and paper diary and should return for Visit 11 (the ‘End of Taper Period’ visit), if possible. Patients who have completed all of the scheduled study visits will be offered the option of entering an OLE. Entry is to be on the same day as Visit 10 (Day 113). Patients not entering the OLE at this visit will be given a 10-day supply of IMP (if required) and instructions for tapering the dose, during which time IVRS and paper diary information will continue to be recorded.
	

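### The Visit 10 pregnancy test, which also serves as the B1 test, is serum only at the central laboratory; an on-site dipstick before open-label dispensing would be a cheap safety improvement

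*Protocol*

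**What the plan says.** **Visit 10.** Section 9.1.1.10, in the V3 wording of Amendment 2, calls for "a pregnancy test (using a serum sample, if appropriate), to be performed by the central laboratory". The Amendment 3 rows shown do not change it.

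**Visit B1.** Section 9.1.2.1 (V3 wording) carries the end-of-treatment data over as B1 data, including "clinical laboratory samples, serum IGF-1 levels (patients less than 18 years of age) and pregnancy test (if appropriate". A separate B1 pregnancy-test sentence in the V2 column is absent from the V3 column, so the Visit 10 result stands as the B1 test.

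**Other visits.** Section 9.1.1.3 (Visit 3) asks for "a pregnancy test if appropriate (using both a serum sample and a urine dipstick". The V3 texts for Visits 5, 7, 9, B4, B6 and B8 use the same formula, "including a pregnancy test if appropriate (using both a serum sample and a urine dipstick", and B10 also names both methods.

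**Where active drug can start.** At Visit 3, "The first dose of IMP will be administered in clinic". For the OLE, Section 9.1.1.10 (V2 wording in Amendment 1) says "Entry is to be on the same day as Visit 10 (Day 113", and Section 5.3.4 lists drug dispensing "during the blinded phase and Visits B1, B2, B3, B4" and onward. In the example transition schedule (Table 8.1.2-2), the block headed "Patients randomised to placebo group" has an open-label dose of zero on Days 1 and 2 and 5 mg/kg/day from Day 3.

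**The concern.** Patients with no CBD exposure in the trial can start active drug at two points: randomization at Visit 3, and the transition at Visit 10/B1 for those who were on placebo. The first has a serum test plus a dipstick. The second has only a serum sample sent to the central laboratory, yet OLE entry and dispensing happen the same day. Being an end-of-treatment visit does not explain the difference, because B10 closes the first OLE year and has both methods.

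At stake is timing. If the laboratory is slow and nothing elsewhere holds dosing, an early pregnancy in a placebo patient could be exposed to CBD for a few days before the result is available. Efficacy, power and type I error are not touched.

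**Working it through.** **Step 1: test method by visit** (Section 9 visit texts shown; Visit 3 from Amendment 1, the rest from Amendment 2).

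| Visit | Section | Method |
|---|---|---|
| 3 | 9.1.1.3 | serum + dipstick |
| 5 | 9.1.1.5 | serum + dipstick |
| 7 | 9.1.1.7 | serum + dipstick |
| 9 | 9.1.1.9 | serum + dipstick |
| 10 (= B1) | 9.1.1.10, 9.1.2.1 | serum only, central laboratory |
| B4 | 9.1.2.5 | serum + dipstick |
| B6 | 9.1.2.7 | serum + dipstick |
| B8 | 9.1.2.9 | serum + dipstick |
| B10 | 9.1.2.11 | serum + dipstick |

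Eight of nine name both methods; Visit 10 is the exception.

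**Step 2: exposure before the result.** The protocol gives no figure to reproduce. Inputs are the placebo open-label doses in Table 8.1.2-2 for Days 1 to 7, namely 0, 0, 5, 5, 10, 10 and 15 mg/kg/day, and a turnaround of k calendar days from Day 1. The turnaround is my assumption, taken over 1 to 7 days. If the result arrives before the dose on day 1 + k, exposure is the sum of the doses on Days 1 to k.

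| k (days) | Sum | Exposure (mg/kg) | Dosing days |
|---|---|---|---|
| 1 | 0 | 0 | 0 |
| 2 | 0 + 0 | 0 | 0 |
| 3 | 0 + 5 | 5 | 1 |
| 4 | 5 + 5 | 10 | 2 |
| 5 | 10 + 10 | 20 | 3 |
| 6 | 20 + 10 | 30 | 4 |
| 7 | 30 + 15 | 45 | 5 |

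The only turnaround in the document is superseded V1 wording for Visit 1, 3 to 5 working days. It does not govern Visit 10 and serves only to place the assumption. Three working days is 3 calendar days from a Monday or Tuesday and 5 from a Wednesday, Thursday or Friday; five working days is 7 calendar days. That span of 3 to 7 days corresponds to 5 to 45 mg/kg.

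**Step 3: age of the previous test.** Visit 9 is Day 85 and Visit 10 is Day 113, so 113 − 85 = 28 days. Adding 2 days to reach transition Day 3 gives 30. With ±3 days on each visit the range is 30 − 6 = 24 to 30 + 6 = 36 days.

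**Step 4: who is affected.** The planned placebo group is 210 / 3 = 70. Only those who enter the OLE and for whom a pregnancy test applies count. That fraction is not stated, so 70 is a ceiling well above the likely number.

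**The case against.** Four points weigh on the other side.

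1. No text shown says that a dipstick is read on site or before dosing. The B4, B6 and B8 sentences pair the dipstick with central-laboratory analysis, and Visit 3 says only that samples are taken. This stands. A reader might infer that Visit 3 has a same-day check that Visit 10 lacks, or that copying the dual-method phrase to Visit 10 would close the gap. The documents support neither, so the fix needs an explicit reading rule.

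2. Serum is the common method. The V3 synopsis and Section 9.2.9 speak only of serum tests, and screening at Visit 1 is also serum only. This stands too: Visit 10 contradicts nothing in those places. The contrast lies in the visit texts, and Visit 1 is outside the range compared.

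3. The Visit 10 turnaround is not stated, the dosing table is an example, and the current protocol's main text (Part 1) is not shown and may contain a hold. A reader might infer that the protocol lets placebo patients take CBD before their result is known. The documents do not establish that; with a result within two days, prior exposure is zero.

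4. The added exposure is small beside what the design already accepts. Tests in the maintenance period are 28 days apart, and after B1 the next one in the visit texts is B4 on OLE Day 92. This limits the importance of the point but does not remove it: an on-site check when exposure begins costs very little.

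**Conclusion.** The point holds as a minor, optional improvement. In the V2 and V3 visit texts shown, the test at the second possible start of active drug is the only one from Visit 3 to B10 specified as serum only. Whether any patient would take CBD before the result depends on two things that cannot be checked here: a central turnaround longer than about two days, and no hold in Part 1. If both apply, exposure before the result is 5 to 45 mg/kg over 1 to 5 dosing days for a turnaround of 3 to 7 days, in a small subset of at most 70 patients.

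Existing safeguards limit the risk: the Visit 9 test (serum plus dipstick, nominally 30 days before the first open-label dose), safety calls every two days during the transition, and mandatory withdrawal for pregnancy. It would be wrong to conclude that the Visit 10 test is missing or that a pregnancy would escape detection. The serum test is done at the right visit; only the timing of its result is open.

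**What to change.** In Section 9.1.1.10, with a cross-reference in Section 9.1.2.1, add a urine dipstick for every applicable patient entering the OLE. Apply it in all arms, since allocation is still blinded. State that the dipstick is read on site, with a negative result recorded, before open-label drug is dispensed; the existing dual-method wording does not require this. If no urine is obtained, require confirmation of the serum result before the first open-label dose, which is Day 3 in the example schedule.

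The cost is a sentence or two of protocol text and one dipstick per applicable patient, using urine already collected at Visit 10 where possible. The downside is that a patient who cannot give urine may wait a short time for the serum result before starting open-label drug.
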